## Statistical Power and Statistical Analysis

**Statistical power:** For Aim 1, primary endpoint, with an n=75 and 50 completers, we will have >80% chance of detecting a difference in the rate of BMD AP lumbar spine increase of 0.024g/cm^2/y at a 2-sided  $p=0.05$  level. This compares favorably with the rate of BMD AP spine increase of 0.036 g/cm^2/y in a study by Baum *et al.* administering GH for 18 months to hypopituitary subjects with GH deficiency. This was calculated with software developed by co-investigator [REDACTED] for sample size for random slopes models, available in Matlab [REDACTED]. The variance covariance matrix of the random effects,  $\Psi$ , and residual variance,  $\sigma^2$ , were estimated from longitudinal data from Baum *et al.* that had originally been analyzed by [REDACTED]. The variance of the intercept was 0.024, slope 0.000211, covariance 0.00199 and residual variance,  $\sigma^2$ , 0.00092 and an exponential drop-out rate of 0.36/yr, which is greater than we expect. The program uses the fact that the variance covariance matrix for the fixed effects of the model are:  $\mathbf{V(B)} = \{\mathbf{X}'[\sigma^2] + \mathbf{Z\Psi Z}'\}^{-1}\mathbf{X}$ . One incorporates drop outs by replacing  $\mathbf{X}'[\sigma^2] + \mathbf{Z\Psi Z}'\}^{-1}\mathbf{X}$  by a weighted sum for different follow-up times with weights equal to the follow-up probability -- a special case of the general model described in Pinheiro and Bates. For Aim 2, primary endpoint, with 50 completers we can detect 0.81 x SD of the difference in bone marrow fat content over a year; For secondary endpoints: for trabecular thickness (TbTh) and cortical thickness (CoTh), based on our preliminary data in obese men receiving placebo for 6 months in which the standard deviation (SD) of the change in TbTh was 0.0047mm and of CoTh was 0.0015mm, we will be able to detect an annual increase of 0.008mm and 0.012mm, respectively; for FEA we will have a power of 80% at a two-sided  $p=0.05$  significance level, if the true rate of difference in estimated failure load between the treatments is 316 units, based on an assumption that the SD is 570 units, as derived from Boutroy *et al.* With 50 completers, we will have an 80% power at a 2-sided  $p=0.05$  level to see a difference in PINP of 38.6 ng/ml, total abdominal fat of 50.8 cm^2, lean mass of 1.2 kg, vitamin D of 0.025 ng/ml, hsCRP of 0.025 mg/l, and apoB of 18.6 mg/dl per year. These were calculated from our preliminary data administering GH to obese subjects for 6 months. The power for the mediation analyses (see below) depends on the effect size of the treatment on BMD and on the correlation of the secondary endpoint on BMD. We derived a formula using the delta method. With at least 40 subjects we will have an 80% chance of achieving significance at a two-sided  $p=0.05$  level if the effect size is 2 units and the correlation is 0.5. For the 6-month withdrawal period, we will have adequate power to test whether the BMD remains significantly different from placebo at 24 months. We will have 80% power to detect a difference of 0.04 g/cm^2 assuming that there are at least 43 patients still in the study at 18 months (we expect 50).

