
**Data analysis plan:** We will pool data from men and women using a random slopes model; we will consider a model where each patient has a random slope and intercept. The mean intercept and slope may be different for men and women and in each treatment group. The primary analysis is a pooled analysis of treatment effect across gender with weights equaling the frequency of men and women in the sample. A secondary analysis will test for the significance of the treatment-gender interaction on the rate of change of BMD and all other endpoints. For all analyses, an intent-to-treat analysis will be performed. We plan to apply the guidelines developed by the National Research Council regarding missing data. Our primary analysis, the random slopes model, assumes that data is missing at random. We also will conduct two sensitivity analyses. The first assumes that the missing data is a function of the unobserved random effect and the second tests the assumptions in this model under other missingness mechanisms. We will also determine which of the secondary endpoints appears to mediate the treatment effect on an endpoint, such as BMD, microarchitectural parameters, and bone marrow fat by examining the effect of treatment on the potential mediator and of the potential mediator on the endpoint; examples of this will include whether Pref-1 mediates the effects of GH on bone marrow fat or strength, and whether bone marrow fat, body composition variables, inflammatory markers, lipids or vitamin D mediate the effects of GH on bone strength. The effect on one endpoint by a potential mediator is the product of the two effects. The Sobel test will test whether this effect is zero. As there are no known moderators of GH treatment in this population and the population has been purposely selected for osteopenia, we will not control for covariates other than gender in our primary analysis. We will perform exploratory analyses to answer the following: 1. Among an osteopenic population are there covariates

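### The Sobel test planned for the mediation analyses is conservative at about 50 patients; joint significance with treatment in the second model is a cheap improvement, with a multiplicity cost to state

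*SAP*

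**What the plan says.** The SAP's Data analysis plan will look for mediators "by examining the effect of treatment on the potential mediator and of the potential mediator on the endpoint". It then states: "The effect on one endpoint by a potential mediator is the product of the two effects". For the test of that product it says: "The Sobel test will test whether this effect is zero". No other test is named for these analyses. One example given is "whether bone marrow fat, body composition variables, inflammatory markers, lipids or vitamin D mediate the effects of GH on bone strength". The protocol's Specific Aim 2 hypothesises that the gain in strength runs through such pathways, so these are the tests that address it.

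The plan does not say whether treatment is in the mediator-endpoint model. The one model it does describe is the random slopes model, of which it says: "The mean intercept and slope may be different for men and women and in each treatment group".

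On power, the SAP's Statistical power paragraph says "The power for the mediation analyses (see below) depends on the effect size of the treatment on BMD". It names a second determinant, namely how strongly the secondary endpoint correlates with BMD. It uses a delta-method formula that is not shown. Its claim is: "With at least 40 subjects we will have an 80% chance of achieving significance" at two-sided 0.05, "if the effect size is 2 units and the correlation is 0.5". The unit is not given.

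**The concern.** The Sobel test refers a product of two estimates to a normal distribution. When neither path is estimated very precisely, the product is not close to normal. The test then rejects less often than its nominal level and misses real indirect effects. The SAP sets these tests at two-sided 0.05, so a test that runs at 1-2% leaves much of that allowance unused. At stake is the chance of detecting a true mediator in a trial of 40 to 50 contributing patients. The primary comparisons of BMD and bone marrow fat do not use this test.

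**Working it through.** **Inputs.** From the SAP: at least 40 patients for mediation, 50 expected completers of 75 enrolled, correlation 0.5, two-sided 0.05, and 0.81 SD as the detectable difference in bone marrow fat, a named mediator. Assumed here: 1:1 allocation, one complete change score per patient, 0.5 read as the within-arm correlation, and mediator shifts other than 0.81 SD.

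**1. The SAP's own figure.** Let zA be the expected z for treatment on the mediator and zB that for the mediator on the endpoint. The delta-method statistic is z = zA·zB/√(zA² + zB²), and power is Φ(z − 1.96). Read 2 units as 2 SD (an assumption), with zA = 2√n/2 and zB = 0.5√n. At n=40, zA = 6.32, zB = 3.16 and z = 20/√50 = 2.83, so power is Φ(0.87) = 80.7%. The smallest n reaching 80% is 40. Other standard errors for the second path give 84.0% to 88.5%. The stated 80% can therefore be reproduced, under a reading that the SAP does not spell out.

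**2. Why Sobel is conservative.** The statistic is always below the smaller of zA and zB. If both are 2.5, each path is significant, but z = 2.5/√2 = 1.77, which is below 1.96.

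**3. Power by simulation** (100,000 trials per cell). M = a·T + N(0,1) and Y = b·M + N(0,1). Here b = 0.577, because 0.577/√(0.577² + 1) = 0.5. Treatment is in the second model. Sobel rejects if |z| > 1.96; joint significance rejects if both paths have p<0.05.

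| Shift in mediator (SD) | n=40 Sobel / joint | Loss (points) | n=50 Sobel / joint | Loss (points) |
|---|---|---|---|---|
| 0.81 | 49.0% / 63.8% | 14.8 | 65.9% / 77.1% | 11.2 |
| 1.0 | 67.0% / 79.4% | 12.4 | 82.7% / 89.9% | 7.2 |
| 1.25 | 82.2% / 88.9% | 6.7 | 92.9% / 95.5% | 2.6 |
| 1.5 | 88.4% / 91.2% | 2.8 | 95.3% / 96.3% | 1.0 |
| 2.0 | 91.0% / 91.5% | 0.5 | 96.3% / 96.5% | 0.2 |

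At 0.81 SD the treatment-mediator test alone has 70% (n=40) and 80% (n=50) power. That is a ceiling for joint significance; the rest of any shortfall is sample size. With 60 patients the loss is 7 points at 0.81 SD (78.5% / 85.7%) and between 3 and 4 at 1.0 SD (91.9% / 95.4%).

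**4. False positives, n=50, treatment in the second model.** With no effect of mediator on endpoint, Sobel / joint are 1.3% / 4.0% at 0.81 SD and 2.1% / 4.7% at 1.0 SD. With no effect of treatment on the mediator and correlation 0.5, they are 2.4% / 4.8%.

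**5. Where the gain comes from.** If joint significance is held to Sobel's own false-positive rate (n=50, 0.81 SD), its power is 62% against 66% for Sobel. Over six independent mediators with no effect on the endpoint, the chance of at least one false claim is 1 − (1 − 0.0131)⁶ = 7.6% for Sobel and 1 − (1 − 0.040)⁶ = 21.7% for joint significance. With Bonferroni over six, it is 2.7% for joint significance, and power is 47% against 23% for Sobel under the same correction.

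**6. If treatment were left out of the second model.** With n=50, no mediation, and equal shifts in mediator and endpoint, false positives (Sobel / joint) are 8% / 15% at 0.81 SD, 20% / 29% at 1.0 SD and 98% / 99% at 2 SD.

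**The case against.** The case for leaving the plan alone has four parts.

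- **Effect size.** At 2 SD, the reading that reproduces the SAP's 80%, the choice of test costs under 1 point. The 0.81 SD is a detectable difference for one variable, not an expected effect, and 1.0 SD is an assumption made here. This stands, and it limits the point to mediators that move moderately. But the SAP does not state 2 SD, and it ties the effect size to BMD, whereas the tested product depends on the effect on the mediator.
- **Sample size.** Forty is a floor. The protocol will try to replace dropouts to reach 50 completers, and it asks those who leave after at least 9 months to attend a final visit identical to the 18-month one. If 50 of 75 complete at a constant dropout rate, about 75 × √(50/75) = 61 reach 9 months, though not all would attend and their exposure is shorter. This stands: 11 and 7 points at n=50 are the fair headline figures, and they shrink if more patients contribute.
- **False positives.** A conservative test is defensible when many mediators are tested without stated multiplicity control. This stands as a cost, so the fix must deal with multiplicity openly.
- **Validity of the replacement.** Without treatment in the second model, joint significance is worse than Sobel. This stands as a condition of the fix.

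Three stronger readings are tempting, and the documents do not support them. A reader might infer that every mediation analysis uses Sobel, but the exploratory IGF-1 mediation names no test and lies outside this point. A reader might infer that treatment is omitted from the second model. The SAP is only silent there, and its stated model lets intercept and slope differ by treatment group. A reader might infer that the 80% is wrong; step 1 shows a simple reading that yields it.

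**Conclusion.** The point holds as a cheap improvement to the mediation analyses that use the Sobel test. At the expected 50 completers, Sobel gives up about 11 points of power at 0.81 SD on the mediator and about 7 at 1.0 SD. At 1.5 SD the loss is 1-3 points over 40-50 patients. Joint significance stays within the nominal 5% in the settings simulated, provided treatment is in the second model. It makes use of the stated 5%; it is not a more efficient test at equal error.

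The figures rest on equal arms, single complete change scores and a within-arm correlation of 0.5. Repeated measures and dropout were not simulated. If 0.5 is the overall correlation instead, the loss over 40-50 patients and 0.81-1.0 SD is 9.9-16.9 points. The missing unit in the mediation power statement is a matter for clarification only.

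**What to change.** In the Data analysis plan, replace the Sobel sentence with a joint-significance rule. Mediation is claimed only if treatment on the mediator has p<0.05 and the mediator on the endpoint has p<0.05 in a model that also contains treatment. Keep both conditions in one sentence, because the second is what makes the rule valid.

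Report a percentile bootstrap interval for the indirect effect, resampling whole patients rather than visits, as an estimate only. Used as a test at n=50 it runs slightly above 5% (5.6% at 0.81 SD, 6.1% at 1.0 SD).

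Either apply Holm to the larger of the two p-values across the mediators of one endpoint, or label the mediation results as not controlled for multiplicity. In the Statistical power paragraph, define the 2 units and say whether the effect is on BMD or on the mediator.

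The practical cost is a few sentences and little computing. The statistical cost is a per-test false-positive rate of about 4% instead of about 1% (n=50, 0.81 SD), and the familywise rise shown above if no multiplicity control is adopted.

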Briefly describe study design and anticipated enrollment, i.e., number of subjects to be enrolled by researchers study-wide and by Partners researchers. Provide a brief summary of the eligibility criteria (for example, age range, gender, medical condition). Include any local site restrictions, for example, "Enrollment at Partners will be limited to adults although the sponsor's protocol is open to both children and adults."

Over the five years of this proposal, we expect to screen 300 patients in order to enroll 75 (38 healthy women and 37 healthy men) total men and women with obesity, osteopenia and relatively low IGF-1, adiposity for an evaluable 50 subjects. We will attempt to replace subjects who have dropped out of the study to ensure 50 completers at 18 months (for which the study is powered).

Eligibility:

Subjects will undergo a pre-study screening visit to determine eligibility for the study.

Inclusion criteria:

- Ages 18-65 and generally healthy
- $BMI \ge 25 \text{ kg/m}^2$

Partners Human Subjects Research Application Form Version Date: June 1, 2005

- BMD T or Z-score \leq -1.0 (as measured by DXA)
- IGF-I within or below the mean (plus 10% above the mean) for age and gender **Exclusion criteria**
- For women: amenorrhea for 3 months or more if premenopausal, pregnancy or breastfeeding, polycystic ovary syndrome
- Elevated creatinine or TSH levels; alanine amino transferase levels greater than 2 times the upper limit of normal
- History of diabetes mellitus, cancer or other serious chronic disease
- Use of osteoporosis medications
- Medication that could affect bone metabolism within the past three months, such as chronic oral glucocorticoids, gonadal steroids, or anticonvulsants
- Hct > 5 units below the lower limit of normal
- Routine MRI exclusion criteria including the presence of pacemaker or cerebral aneurysm clips
- Osteoporosis, that, according to WHO classification (BMD T score less than or equal to 2.5 at the AP spine, total hip or femoral neck), would warrant treatment consideration.

Briefly describe study procedures. Include any local site restrictions, for example, "Subjects enrolled at Partners will not participate in the pharmacokinetic portion of the study." Describe study endpoints.

Screening Visit: (n=300: 150 healthy obese women and 150 healthy obese men)

- A complete medical history, physical examination, height, weight, waist and hip circumferences. Calculation of BMI, waist:hip ratio.

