- Fasting glucose, HbA1c, IGF-1, TSH, creatinine, SGPT, urine pregnancy test, HCT, Ghrelin
- DXA scan to evaluate for osteopenia and body composition
- Measurement of bone age for males 18 or 19 years old

Study Visits:

1. Baseline: (n=75: 38 healthy obese women and 37 healthy obese men)

The baseline visit will occur within 8 weeks after the screening visit. The following assessments will be made during the baseline visit days and will occur within a 30-day period.

- Assessment of potential factors affecting BMD: family history of osteoporosis, alcohol, free testosterone, estradiol, exercise (Paffenbarger Physical Activity Questionnaire and Modified Activity Questionnaire (MAQ)), Calcium & Vitamin D Intake (Calcium & Vitamin D Frequency Questionnaire), and food diary log
- Waist circumference, weight, and BMI
- 2-hour GHRH-arginine GH stimulation testing

Partners Human Subjects Research Application Form Version Date: June 1, 2005

- CT
- DXA scan (only if baseline occurs more than 6 weeks after screening visit)
- Xtreme CT
- Head x-ray if subject reports possibility of metal in face or head
- MRI/MRS
- Blood drawn to determine levels of hormones and other chemicals
- Oral glucose tolerance test (OGTT)
- Functional Strength Test

2. Follow-up visits:

The following assessments will be made during the 6 week, 3 month, 4.5 month, 6 month, 9 month, 12 month, 15 month, 18 month and 24 month visits. The 3 week, 9 week, and 4 month visits will be performed during a \pm 2 week interval around the indicated return time to allow for potential scheduling conflicts. The 6 month, 9 month, 12 month, 15 month, 18 month and 24 month visits will be performed during a \pm 1 month interval around the indicated return time. Subjects who drop out or are discontinued from the study after participating for at least 9 months will be asked to come in for a final study visit that will be identical to the 18-month study visit. The follow-up visits involve:

- Medical history, physical examination, weight, waist and hip. Return menses (for women), growth hormone dosing records, and all study medication vials.
- DXA scan (12 month, 18 month, and 24 month visits)
- CT scan (18 month visit)
- Low-dose CT for body composition only (6 month visit)*
- Xtreme CT scan (12 month, 18 month, and 24 month visits)
- MRI/MRS (6 month visit* and 18 month visit)

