- Blood drawn to determine levels of hormones and other chemicals (3 week, 9 week, 4 month, 6 month, 9 month 12 month, 15 month, 18 month and 24 month visits).
- OGTT (6 month, 12 month, and 18 month and 24 month visits)
- Paffenbarger Physical Activity Questionnaire and Calcium & Vitamin D Frequency Questionnaire (6-month, 12-month, 18-month, 24-month visits)
- Functional Strength Test (6-month, 12-month, 18-month and 24-month visits)
- Food diary log (18-month visit)

	-	0	
-			
•			
-			

*discontinued performing starting in August 2017

Study endpoints

Aim 1:

Primary Endpoint: Change in BMD over 18 months in the GH vs placebo group.

Secondary Endpoints:

- 1. Bone microarchitectural parameters
- 2. Bone strength by FEA

Aim 2:

Primary Endpoint: Change in bone marrow fat in the GH vs placebo group. **Secondary Endpoints:**

- 1. Pref-1.
- 1. Bone formation markers P1NP, ucOC.
- 2. Fasting and 2-hour OGTT insulin.
- 3. Inflammatory markers hsCRP, TNF1 receptor, and IL-6.
- 4. Serum lipoproteins.
- 5. 25-OH vitamin D.

Dual-energy X-ray-absorptiometry (DXA): DXA will be used to measure BMD of the AP and lateral spine (L1-L4), distal radius, total hip, femoral neck and total body. Total fat and fat-free mass measurements will also be obtained.

Quantitative computed tomography (QCT): As DXA may overestimate BMD in obesity,¹⁰⁷ we will perform volumetric QCT of L1 and L2 and of the proximal femur (GE LightSpeed Pro CT scanner, GEHealthcare, Waukesha, WI or Somatom Definition, Siemens Healthcare, Forchheim Germany) and low-dose single slice CT of the abdomen and thigh for body composition.

High-resolution CT: High resolution peripheral QCT will be used to measure volumetric density, morphology and microarchitecture at the distal radius and distal tibia (XtremeCT, Scanco Medical AG[®], Bassersdorf, Switzerland). The outcome variables computed by automated analysis will include volumetric BMD (g hydroxyapatite/cm³) for total, trabecular, and cortical regions; cortical thickness (µm) and porosity measures and trabecular number (mm-1), thickness (mm), and separation (mm). HR-pQCT measurements will be performed at the non-dominant wrist and leg in the absence of a history of fracture.

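### The primary BMD slope model adjusts for gender only, and neither stated reason justifies leaving out age and menopausal status as prognostic factors; the likely cost is a small loss of precision

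*SAP*

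**What the plan says.** The Aim 1 primary endpoint (Protocol, Study endpoints) is "Change in BMD over 18 months in the GH vs placebo group". The SAP's Data analysis plan fits a random-slopes model in which every patient has a random intercept and slope, and the mean intercept and slope may differ by sex and by treatment group. The treatment effect is pooled over sex, weighted by the sample frequencies of men and women.

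On other baseline covariates, the SAP gives its reasons and its decision in one sentence: "As there are no known moderators of GH treatment in this population and the population has been purposely selected for osteopenia", and so "we will not control for covariates other than gender in our primary analysis". Covariates are otherwise left to exploratory stepwise analyses. The examples listed there include estradiol and free testosterone but neither age nor menopausal status.

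Eligibility in the Protocol is broad: "Ages 18-65 and generally healthy". The reproductive exclusion for women covers "amenorrhea for 3 months or more if premenopausal". It is thus limited to premenopausal women, and no criterion excludes postmenopausal women. Planned enrolment is "38 healthy women and 37 healthy men".

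**The concern.** Two different roles of a covariate are run together. A moderator changes the treatment effect. A prognostic factor changes the outcome whatever the treatment. Having no known moderators is a reason not to plan treatment interactions, but it says nothing about whether age or menopausal status predicts the untreated rate of BMD change. Selection for osteopenia restricts the level of BMD at entry, while the endpoint is how BMD changes afterwards.

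All women from 18 to 65 therefore share one mean slope per arm. If untreated slopes differ between pre- and postmenopausal women, that difference goes into the between-patient slope variance and widens the standard error. An arm that happens to receive more postmenopausal women is not adjusted for it. At stake is some of the power for the primary comparison, which the SAP puts at just over 80%.

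**Working it through.** **Inputs from the SAP (Statistical power).** Random-effects matrix Ψ: intercept variance 0.024, slope variance 0.000211, covariance 0.00199. Residual variance σ² = 0.00092. N = 75 with 50 completers. Target 0.024 g/cm2/y, two-sided 0.05.

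**Input from the Protocol.** DXA at baseline, 12 and 18 months (the 24-month scan is left out).

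**Assumptions.** 1:1 allocation (37.5 per arm). Drop-out at the rate that leaves 50 of 75 at 18 months: ln(75/50)/1.5 = 0.27 per year. Women are half the sample and half of them are postmenopausal. Their untreated slopes differ from those of premenopausal women by d = 0.01 to 0.03 g/cm2/y.

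**1. The plan's own figure.** V(B) = {Σ X′[σ²I + ZΨZ′]⁻¹X}⁻¹, with separate baseline means by arm, gives SE = 0.00856 for the slope difference. Power = Φ(0.024/0.00856 − 1.96) = Φ(0.844) = 80.1%, which agrees with the SAP. The figure depends on the scan schedule, which the power paragraph does not state. With the SAP's own drop-out rate of 0.36 per year, the 0/12/18-month schedule gives 75.7% to 77.6%, and six-monthly scans to month 18 give 79.1% to 81.3%, depending on how baseline means are modelled.

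**2. If the heterogeneity adds to the stated slope variance.** Within women, a half-and-half mixture adds 0.25d². Averaged over both sexes, the addition is 0.5 × 0.25 × d².

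| d (g/cm2/y) | Added slope variance | Share of 0.000211 | SE | Variance removable, 1 − (0.00856/SE)² | Power for 0.024 |
|---|---|---|---|---|---|
| 0 | 0 | 0% | 0.00856 | 0% | 80.1% |
| 0.01 | 0.0000125 | 6% | 0.00861 | 1.2% | 79.6% |
| 0.02 | 0.0000500 | 24% | 0.00877 | 4.7% | 78.1% |
| 0.03 | 0.0001125 | 53% | 0.00902 | about 10% | 75.8% |

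**3. If it is already inside the stated variance.** With the covariance held at 0.00199, the slope variance cannot fall below 0.00199²/0.024 = 0.000165, or Ψ is no longer a valid covariance matrix. Reducing it to about that floor (0.000166) gives SE = 0.00837 and power Φ(0.024/0.00837 − 1.96) = Φ(0.907) = 81.8%, against 80.1%. With 50 completers and a common baseline mean, the same step moves power from 79.5% to 81.5%. The gain is at most about 2 points.

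**4. Chance imbalance.** With 19 women per arm, the SD of the difference in postmenopausal share is √(2 × 0.25/19) = 0.162. At d = 0.02 and half weight for women, one SD shifts the pooled slope difference by 0.162 × 0.5 × 0.02 = 0.0016, or 7% of 0.024. Two SDs shift it by 0.0032, or 13%. This is not an extra loss. The variance added in step 2 at d = 0.02 is 0.00877² − 0.00856² = 3.6 × 10⁻⁶. The variance of the imbalance shift is 0.0016² = 2.6 × 10⁻⁶ with the women at entry, and 0.002² = 4.0 × 10⁻⁶ with 25 women completing. They are the same quantity.

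**5. Price of adjusting.** Two further slope terms (age by time, menopausal status by time), with 75 patients and four sex-by-arm mean slopes, cost about 2/(75 − 4) = 2.8% of variance if they explain nothing. The SE becomes 0.00856 × √1.028 = 0.00868 and power Φ(0.024/0.00868 − 1.96) = 79.0%. Set against step 2, the net change in power from adjusting is about −0.6, +0.9 and +3.2 points at d = 0.01, 0.02 and 0.03. Any variance explained by age would add to these; the documents give nothing from which to size it.

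**The case against.** The strongest reply is that no error has been shown. A parsimonious, prespecified model for 75 patients is a legitimate choice. Differing natural courses are carried by the random slopes, so the standard error already allows for them. With random allocation, the slope difference is unbiased and the test keeps its level. That stands: the point is one of efficiency and of a rationale that does not fit the decision.

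Several stronger readings are tempting and are not supported:

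- *That eligible groups have opposite natural BMD courses.* The documents describe no untreated slopes by age or menopause. The screening item "Measurement of bone age for males 18 or 19 years old" has no stated purpose and does not show rising BMD.
- *That slopes may differ only by sex.* Mean slopes also differ by arm, and every patient has a random slope. Sex is the only baseline covariate in the fixed effects.
- *That nothing guards against imbalance.* The text available for this review does not describe allocation, and part of the SAP was not supplied, so stratification by age or menopause cannot be ruled out. Stratifying would limit imbalance, though it would not put the factor in the model.
- *That a two-SD imbalance is a further harm.* It is part of the same variance and its direction is random.

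The extra variance may also be double-counted if the stated 0.000211 already contains it. Step 3 covers that case.

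**Conclusion.** The point holds as a minor, optional improvement. Neither reason in the SAP supports leaving age and menopausal status out as prognostic terms for a rate-of-change endpoint. The consequence is lost precision and unadjusted chance imbalance, not bias or an invalid test, provided allocation is random.

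On the assumed slope differences, the omission costs about 0.5, 2 or 4 points of power (80.1% down to 79.6%, 78.1% or 75.8%). If the heterogeneity is already in the stated variance, adjustment gains at most about 2 points. After allowing for the added terms, adjustment is close to neutral at a difference of 0.01 g/cm2/y and worthwhile from about 0.02 upwards. The slope differences, the share of postmenopausal women and 1:1 allocation are all assumptions. The weakness of the stated rationale does not depend on them.

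**What to change.** Before unblinding, amend the Data analysis plan as follows:

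- Add baseline age and menopausal status, each with a time interaction, to the primary random-slopes model as prognostic terms. Define menopausal status in writing, including how perimenopausal women are classed.
- Keep a common treatment effect on slope, or the existing weighting by sex only. Do not add treatment terms for a third group, which on the assumption above would rest on roughly 9 or 10 women per arm at entry.
- Replace the moderator rationale with one that addresses prognosis.
- Report the gender-only model as a sensitivity analysis.

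The cost is SAP wording and a few degrees of freedom: roughly 3% more variance, or about one point of power, if natural slopes do not differ. No new visits or assessments should be needed. Age is an eligibility item, and menopausal status has to be known to apply the amenorrhea exclusion. It is not a listed baseline item, however, so the team should confirm that it was recorded for every woman.
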